## K. Assessment of Subject Safety and Development of a Data and Safety Monitoring Plan

### K1. Data and safety monitoring plan

- a. **Persons/groups who will review the data:** The PI, investigative team, and the DSMB will monitor data regarding recruitment, retention, and safety. The DSMB will consist of three individuals, not otherwise affiliated with the trial, who have the relevant expertise to monitor the study progress and participant safety. This includes individuals with expertise in nutrition and dietary intervention for weight loss, general medicine in rural settings, and exercise physiology and physical activity. The members and qualifications of the DSMB are as follows:

[name] is Professor and Chair of the Department of Dietetics and Nutrition at KUMC and Director of the nutrition core for the Clinical and Translational Science Unit. She has extensive experience in conducting diet and behavior modification interventions as well as measuring dietary intake of diverse populations. [name] has led the nutrition components of numerous NIH R01-funded obesity intervention trials over the past 16 years, including overseeing all nutrition safety issues.

[name] is an Associate Professor in the Department of Family Medicine at KUMC and a physician-scientist with clinical and research responsibilities. He has developed and evaluated cross-cultural communication interventions for healthcare providers who serve underserved populations. His prior research includes an intervention study in 5 rural clinics in mid-Missouri to promote better self-management of diabetes, during which time he learned first-hand how to solve recruitment and retention challenges.

[name] is Professor and Chair of the Department of Kinesiology at Kansas State University. He is an exercise physiologist with a research program investigating cardiopulmonary limitations to exercise and the environment. He is NIH funded, Associate Editor-in-Chief for Medicine and Science in Sport and Exercise, and a Fellow of the American College of Sports Medicine.

- b. **Data/events that will be reviewed:**

Participant accrual. The DSMB will review study enrollment to help assure recruitment goals are met.

Participant attrition. Attrition will be reviewed at least monthly by the investigative team, and bi-annually by the DSMB. If the DSMB has concerns about whether attrition has reached a level that may inhibit the primary aim, they may initiate a conference call with investigators to discuss methods for improving retention.

Serious adverse events. The number and nature of all SAEs, unmasked to treatment condition, will be reviewed.

- c. **Frequency of review:** The DSMB will meet twice per year until active intervention with study participants is completed. The PI, designated staff, and study statistician (as needed) will prepare and present data reports to the DSMB. The DSMB will review all related serious adverse events both during scheduled meetings and during interim contacts for fatal or life threatening serious adverse events.

**d. Types of analyses to be performed:** Enrollment and attrition numbers will be presented as a percentage of the overall goal and broken down by institution and by primary care site. Number of SAEs will be tabulated, and the Serious Adverse Event Record Form will be included for each serious, related event. The DSMB will identify any needed modifications to data parameters and format as the study progresses.

**e. Safety-related triggers that would cause the PI to stop or alter the study:**

Stopping rules regarding recruitment and retention. Given the low risk nature of this diet and exercise trial, the most likely scenario for stopping the trial would be failure to recruit or retain participants. We have strategies in place to continually assess and improve recruitment and retention. The DSMB will review retention and initiate a meeting if needed with the investigative team to devise additional strategies to improve recruitment and retention if needed. If enrollment is 50% or less of goal by 3 years, or if attrition exceeds 30%, the DSMB will determine if the study should continue.

Stopping rules regarding exercise-related SAEs. Risk estimates of major cardiovascular events during strenuous exercise range from 0.3 to 2.7 events per 10,000 person-hours for men and 0.6 to 6.0 events per 10,000 person-hours for women. The DSMB will review serious cardiovascular events related to study participation, evaluate the expected likelihood based on the current enrollment numbers and estimates of exercise person-hours, and determine if the study should continue. Other unanticipated situations may warrant stopping the trial; accordingly, the DSMB will review all serious adverse events.

## **K2. Serious Adverse Event reporting**

Surveillance for serious adverse events (SAEs) will occur at 6, 12, 18, and 24 months using a participant self-reported medical history update survey form. In addition, participants may report SAEs to practice or central study staff at other time points, e.g., during assessment visits, counseling sessions, retention contacts, and routine clinical care. All serious adverse events will be documented via a SAE Record Form. The form will capture information to include the date of onset, the date no longer serious, who first learned of the event and how, a description of the event, a classification of the seriousness, the outcome, and evaluation of the potential relationship to the intervention, and if at least possibly related, an evaluation of the expectedness.

Practice or central study staff, to include KUMC staff, who first become aware of the SAE will be responsible for initiating the SAE Record Form in REDCap. Central study staff and practice personnel have been asked to make a good faith effort to initiate the SAE Record Form within 2 business days of learning of the event. In some instances, however, meeting this two business day time frame may be difficult. Information obtained via online or hard copy surveys (patient self-report of hospitalizations) needs to be corroborated with the practice and/or patient before the report is initiated, to ensure the event was a true SAE (e.g., overnight hospitalization). Information provided by patients communicating with study counselors or practice staff may need to be corroborated via medical record review prior to reporting; this may take additional time especially if the hospitalization occurred at a facility not directly affiliated with the study practice; i.e., additional time may be needed to obtain hospital admit and discharge summaries prior to initiating the report. Given the noted circumstances, a delay in the reporting time period may be understandable in some instances. Given the minimal risk posed by the study intervention, a delay in initiating the report can be accepted if all parties act in good faith and attempt to maintain reporting timelines to the extent feasible.

Once the SAE Record Form is initiated, the KUMC Lead Coordinator will work with central study staff and practice personnel to collect any missing information on each event and complete each SAE report as soon as possible. This will include, confirming, in consultation with the site PCP and PI, and the KUMC study physician as needed, the evaluation of potential relationship to the intervention. Site physicians will make the final determination of study relatedness. The PI and Lead Practice Coordinator will help ensure adequate information is included in the description of the event for the DSMB to review the evaluation of study relatedness. Upon completion of an SAE Report, KUMC will report to the DSMB according to the timeframe described below and to the KUMC IRB in accordance with IRB guidelines. Non-serious adverse events will not be tracked or reported as part of safety monitoring activities.

Type of Data	Report to DSMB after SAE form completed	Timeline of DSMB Review	Data Reviewed By
All serious adverse events, enrollment, and retention; total and by site	Bi-annually	Bi-annually	Entire DSMB
Life-threatening or fatal SAEs— independent of relatedness, unexpectedness	Within 1 working day	Within 1 week of SAE report	DSMB Chair or entire DSMB at discretion of Chair
Related and unexpected SAEs	Within 1 working day	Within 1 week of SAE report	DSMB Chair or entire DSMB at discretion of Chair
Related and expected SAEs	Within 5 working days	Within 2 weeks of SAE report	DSMB Chair or entire DSMB at discretion of Chair

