**Demographic information.** Information will be collected at baseline on date of birth, race, ethnicity, income, marital status, level of education, employment status, time off work for study counseling visits, physical address, insurance status and type, and years living in rural area. Updates will occur at 12 and 24 months.

**Medical history.** Self-reported medical history, including smoking and weight loss history will be collected at baseline. At each follow-up questionnaire, patients will be asked to report hospitalizations/serious adverse events, exercise-related injuries/illnesses, and changes to smoking status. Any serious adverse events reported by patients via the self-reported medical history will be followed up on by KUMC study personnel (see Section I6).

**Medication Information.** Baseline medications will be collected through a phone interview after the patient has signed the baseline survey consent (see Section III C1). Changes in medications will be self-reported at 6mo, 12mo, 18mo, and 24mo.

**SF-12** (general quality of life) is a 12-item survey that measures physical and mental health-related quality of life. The SF-12 is a shortened version of the original SF-36, which has been established as a reliable and valid measure of quality of life and has been widely used, however has been insensitive to quality of life based on BMI and weight change over time. The SF-12 has been shown to detect differences in quality of life among overweight and obese individuals when compared to normal weight controls.

**Impact of Weight on Quality of Life-Lite (IWQOL-L)** is a 31-item self-report measure specifically designed to measure the effects of weight on quality of life that is an abbreviated version of an original 74-item IWQOL measure. The IWQOL-L assesses five domains of functioning: physical function, self-esteem, sexual life, public distress, and work and responses are measured on a 5 point Likert scale from "never true" to "always true." The measure yields a total score and five subscale scores. For overweight/obese samples, the IWQOL-L has demonstrated reliability and internal consistency, construct validity, and discriminant validity when compared to other quality of life measures, detects quality of life changes in response to weight loss during an intervention, and distinguishes differences in quality of life based on BMI.

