## F. Risk Benefit Assessment

### F1. Physical risks to participants

**Exercise.** Risks in this study are primarily related to exercise, an intervention component in all three study arms. Moderate intensity physical activity has few serious risks especially for those with clearance from a medical provider. Physical activity may cause temporary discomfort associated with exertion, muscle soreness, or musculoskeletal injuries. Accidents with physical activity, such as falls or sprained ankles, are also possible. In the DPP study, the occurrence of musculoskeletal injuries was 3% higher in the lifestyle intervention compared to the placebo control arm. Some risk for cardiovascular complications exist for participants with cardiovascular risk factors (e.g., history of MI, hypertension, diabetes). Maximum risk estimates of major cardiovascular events during strenuous exercise are 0.6 to 6.0 events per 10,000 person-hours for women and 0.3 to 2.7 events per 10,000 person-hours for men. However, exercise of all levels is beneficial for reducing cardiac events overall (both at rest and during exercise).

**Diet.** The dietary recommendation for all three study arms is  $\geq 1,200$  kcal/day and therefore avoids the risks associated with very low calorie diets. Although not common in this type of program or this level of caloric intake, calorie restriction can lead to inadequate nutrition or rapid weight loss. Rapid weight loss (>3 lbs per week for several weeks) typically associated with very low calorie diets, unlike the one used in this intervention, may lead to gallstones. Some patients with diabetes may be susceptible to hypoglycemia. Weight loss also has the potential to increase risk of hypotension for patients who are using medications that lower blood pressure.

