Participants will be educated about symptoms of hypotension and hypoglycemia and urged to contact their PCP if they have these symptoms. Overall management of diabetes, hypertension, and cardiovascular disease will remain under the control of the participant’s PCP. All laboratory results obtained as part of study visits will be sent directly to the PCP. The analyzing laboratory and PCP will follow their standard operating procedures for notification and management of critical and panic laboratory values. The practice will provide the laboratory results to KUMC upon receipt. If participants indicate any injury or illness on their medical follow-up form (6, 12, 18, 24 months) that may indicate a safety risk for participation, the study team will follow-up with the participant and the treating PCP as needed.

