### **G. Location Where the Study Will Be Performed**

This is multi-site study that will be completed in collaboration with three academic medical institutions, KUMC, the University of Nebraska Medical Center (UNMC) and the Marshfield Clinic in Wisconsin. KUMC, UNMC, and Marshfield Clinic will be responsible for coordinating study activities in practices affiliated with their institution (see Section I). Across all arms, personnel at the primary care practices will collect informed consent and conduct assessment visits. Across all arms, self-reported questionnaires will be collected outside of the in-person assessment visits, via online forms in REDCap or by mail for those patients without internet access. The location of counseling sessions will vary by arm: **FFS** participants will receive counseling sessions at their primary care practice. **PCMH** participants will receive counseling sessions from primary care clinic personnel, in-person at the primary care practice for the first four months and subsequently via group conference call. **DM** participants will receive counseling sessions via group conference calls conducted by KUMC personnel. *Participant electronic research records* will be stored on the secure REDCap database, developed and overseen by KUMC Medical Informatics. Hard copy forms will be stored long-term in a secure locked file cabinet at KUMC.

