### K3. Patient safety

If central study personnel become aware of new or worsening medical symptoms through information reported by patients during retention phone calls or during counseling sessions in the DM arm, they will refer the patient back to their PCP. Study laboratory results will be sent directly to the PCP per their standard operating procedures. Panic or critical value laboratory results will be managed per their standard operating procedures as well. All providers will be trained in SAE reporting during the central training and in ongoing discussions with the practice throughout the course of the study. Overall management of diabetes, hypertension, cardiovascular disease, and other medical conditions remains under the control of the treating PCP. The treating PCP, in communication with the KUMC PI and study physician, will determine if it is unsafe for the participant to remain in the study based on a change in medical status.

***Exercise-related AEs.*** If a cardiovascular event occurs during prescribed exercise, the physical activity component of the intervention may be suspended and/or later resumed with possible modifications after approval from the treating PCP. For exercise-related events and injuries for patients in the DM arm, the study clinician and/or the treating PCP will be consulted according to the symptoms reported. If appropriate, the participant’s exercise goals or type will be modified. If the symptoms or injury do not resolve after an appropriate period of time, the participant will be referred to his or her PCP for further evaluation and may

be removed from the study. In the FFS and PCMH arms, management of any non-serious exercise-related AEs remains under the control of the PCP.

*Diet-related AEs.* If participants suffer negative health consequences from consuming nutritionally inappropriate diets (such as rapid weight loss, gallstones) and counseling to change nutritional intake have been ineffective, the treating PCP (in consultation with the central counselors for the DM arm) may decide to suspend the intervention. This scenario is uncommon but may occur.

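### Exercise injuries are surveyed identically in all three arms, but no by-arm summary of the non-serious ones is planned for the DSMB or the final report

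*Combined protocol and SAP*

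**What the plan says.** Section II.F1 states: "Risks in this study are primarily related to exercise, an intervention component in all three study arms". It lists soreness, musculoskeletal injury, falls and cardiovascular complications, and reports that in an earlier diabetes-prevention trial "the occurrence of musculoskeletal injuries was 3% higher in the lifestyle intervention compared to the placebo control arm".

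Section II.E2e (Medical history) provides the data: "At each follow-up questionnaire, patients will be asked to report hospitalizations/serious adverse events, exercise-related injuries/illnesses, and changes to smoking status". Table 5 schedules these updates at 6, 12, 18 and 24 months. Section II.G confirms a common route: "Across all arms, self-reported questionnaires will be collected outside of the in-person assessment visits". Section II.I2 has the coordinating centre distribute the questionnaires for all 36 practices.

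Section II.K2 then sets the rule: "Non-serious adverse events will not be tracked or reported as part of safety monitoring activities".

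Three provisions limit what that rule does:

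- II.K1, on the DSMB: "The number and nature of all SAEs, unmasked to treatment condition, will be reviewed". The same section has the DSMB weigh serious cardiovascular events linked to participation against an expected likelihood.
- II.F1, on survey answers: "If participants indicate any injury or illness on their medical follow-up form (6, 12, 18, 24 months) that may indicate a safety risk". In that case the study team follows up with the participant and, as needed, the treating PCP.
- II.K3, on handling outside the survey: "In the FFS and PCMH arms, management of any non-serious exercise-related AEs remains under the control of the PCP". In the DM arm the study clinician, the treating PCP or both are consulted.

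The analysis plan in II.C1 names no injury or safety outcome.

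**The concern.** The protocol identifies a risk, collects information on it in the same way in every arm, and then plans no aggregate use of the non-serious part. K2 gives an overnight hospital stay as its example of what makes an event serious. A sprain or fall that does not lead to admission would therefore normally fall under the exclusion.

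The arms share the same activity advice (II.E2a) but differ in who delivers it and how closely it is overseen: the PCP or a supervised colleague in FFS, clinic staff in PCMH, and a remote counsellor in DM. Section II.I4 says that differences in training and quality control are kept by design, and II.A says the results may warrant a new standard of care. A reader choosing between these models would want to see whether minor exercise injuries differed. As written, neither the DSMB nor the final report is due to receive that description.

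**Working it through.** **Step 1. Follow each kind of information through the plan.**

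| Information | Same ascertainment in all arms? | Individual follow-up | DSMB | Analysis plan (II.C1) |
|---|---|---|---|---|
| Serious events | Survey is common; other routes vary | Yes | Yes, unmasked to condition (K1) | Not named |
| Non-serious exercise injuries on the questionnaire | Yes (E2e, G, I2) | Yes, where a safety risk is suggested (F1) | Excluded (K2) | Not named |
| Non-serious exercise events learned of elsewhere | No; handling differs by arm (K3) | PCP in FFS and PCMH; study clinician and/or PCP in DM | Excluded (K2) | Not named |

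The gap is the second row. The third row shows why a comparison should rest on the questionnaire item alone.

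**Step 2. Reproduce the plan's own figure.** The documents give no figure for any safety comparison. The only precision statement is the 80% power for weight in II.C3, which serves to check the clustering formula.

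- Inputs (II.C3): 12 practices of 40 per arm, ICC 0.05, SD 8 kg, difference 2.75 kg, alpha 0.025.
- Design effect = 1 + (40 − 1) × 0.05 = 2.95.
- Effective n per arm = 480 / 2.95 = 162.7.
- Power with two-sided alpha 0.025 and a normal approximation = 80.5%, which matches the stated 80%.

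**Step 3. Apply the same approach to an injury proportion.**

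- Respondents per arm: 480 × 0.80 = 384, or 384 / 12 = 32 per clinic. This borrows the 80% minimum 24-month retention in II.C1. It is not a stated questionnaire response rate.
- Injury rate p: 10% and 20%, assumed because the documents give no base rate.
- ICC: 0.01 (assumed) and 0.05 (the plan's value for weight).
- Design effect = 1 + 31 × ICC = 1.31 or 2.55.
- 95% half-width = 1.96 × √[2p(1 − p) × design effect / 384].

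| p | ICC 0.01 | ICC 0.05 |
|---|---|---|
| 10% | 1.96 × √(0.18 × 1.31 / 384) = 4.9 points | 1.96 × √(0.18 × 2.55 / 384) = 6.8 points |
| 20% | 1.96 × √(0.32 × 1.31 / 384) = 6.5 points | 1.96 × √(0.32 × 2.55 / 384) = 9.0 points |

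With only 24 clinics in a pairwise comparison, a t reference on 22 degrees of freedom would widen these slightly.

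**Step 4. Vary the assumptions.** With 384 per arm, one arm set 3 points higher, base rates of 5 to 25% and ICC 0 to 0.05, the half-width runs from 3.5 to 10.0 points. With all 480 responding it runs from 3.1 to 9.6.

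**Step 5. Ask whether a test would be useful.** Read the cited 3% as 3 absolute points, which the protocol does not specify. With 384 per arm, p of 10 to 20% and ICC 0.01 to 0.05, power for that difference at two-sided 0.05 is 9 to 21%. The smallest difference detectable with 80% power is 8.1 to 14.4 points. The data support estimation, not a hypothesis test.

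**The case against.** The case for leaving the plan alone has real substance.

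- **The serious part of the risk is covered.** The DSMB sees serious events unmasked to condition and reviews serious cardiovascular events against expectation. A reader might infer from K2 that the trial will have no comparative information on its main risk. K1 does not support that: the gap is confined to non-serious events. This stands.
- **The exclusion is limited.** K2 speaks of safety monitoring. A reader might infer that the injury data can never be compared. Nothing forbids tabulating a questionnaire item by arm; the plan simply does not provide for it. K1 also lets the DSMB change what data it receives. This stands, but a possible request is not a plan.
- **The choice is open and proportionate.** K1 and K2 describe a low-risk trial, individual reports are followed up, and medical clearance is required in every arm. This argues against wider collection of adverse events. It does not argue against using an item already collected centrally.
- **The cited excess transfers poorly.** It compared a lifestyle programme with placebo, whereas every arm here receives the same activity advice. Differences may be smaller than 3%. This stands, and it is a further reason not to propose a test.
- **The data have limits.** They are unblinded self-reports over intervals of up to six months, and the participant judges whether exercise was the cause. The response format is not shown, so coding may be needed. This stands and belongs under cost.

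**Conclusion.** The point holds as a modest reporting gap. K2 excludes non-serious events by an explicit rule, the questionnaire collects exercise injuries in the same way in every arm, and no by-arm summary of the non-serious ones is planned for the DSMB or the final report. The primary weight analysis is unaffected.

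A descriptive table would give each between-arm difference a 95% half-width of about 5 to 9 points. This rests on 384 respondents per arm, assumed injury rates of 10 to 20% and an ICC of 0.01 to 0.05. It could rule out a large excess in one arm. It could not confirm or refute a 3-point excess, and a reader should not take the proposal as a way to test one.

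**What to change.** Amend II.K2 to say, in substance: *Exercise injuries and illnesses reported on the follow-up questionnaires will be tabulated by arm and visit, with response rates, for each DSMB meeting. The final report will describe them by arm, with 95% confidence intervals that account for clinic. Other non-serious events are not tracked.* Add a matching line to II.C1 so that the summary is prespecified, and state that no hypothesis test is planned.

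Use the questionnaire item only, because what study staff learn by other routes depends on the arm (II.K3). The text should note that the item is unblinded self-report.

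The cost is one extra table per DSMB report, one descriptive summary at the end, and coding time if answers are free text. No new data collection is needed, and no rule on participant care changes.
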